6.2 Description of Evaluations

6.2.1 Screening Evaluation

Individuals who contact the site Study Coordinator will be provided information about the study. The Study Coordinator will confirm that the individual is between age 18-60 and is not receiving other interventional or mind-body procedures for their LBP. If the individual is interested in learning more about the project a baseline assessment will be scheduled to obtain informed consent, insure all eligibility criteria are met and schedule a full assessment to begin the study either at that time or within 7 days of the screening evaluation. Before the scheduled baseline assessment, the participant may complete the Oswestry Disability survey to determine if their score is $\geq 20\%$. If the Oswestry score is $< 20\%$, the participant will be notified that they are ineligible for the study and the assessment cancelled.

6.2.1.1 Consenting Procedure

Interested individuals who are scheduled for a baseline assessment will begin the assessment by providing written informed consent using a form approved by the site institutional review board. The consenting process will be conducted by a research assistant who is trained by the Principal Investigator at the site and has completed Biomedical Research Training for Human Subjects research through the Collaborative Institutional Training Institute (CITI) which includes modules on human subjects research ethics and regulations related to informed consent. A copy of the signed informed consent document will be retained by the researchers. A single consent form will be used for the project. The research assistant consenting the participant will sign an Informed Consent Form (ICF) checklist which will be retained by the researchers.

6.2.1.2 Screening

Once informed consent is obtained the following screening procedures will be completed within 72 hours to insure eligibility:

- Confirm age on the date of consent is between 18 – 60 years old.
- Confirm that the participant is not aware that she is pregnant.
- Confirm that the participant is not currently receiving other interventions for their LBP.
- Confirm that the participant is experiencing LBP defined as pain between the 12th ribs and buttock with or without symptoms that extend into the buttock(s) or leg(s). without “red flags” suggesting a possible non-musculoskeletal cause (recent trauma, unexplained weight loss, night pain, systemic illness)
- Participant completes the Oswestry disability index to insure the score is $\geq 20\%$
- Research assistant conducts the physical examination to insure no signs of neurologic deficit are present (positive ipsi- or contra-lateral straight leg raise test (symptoms reproduced $<45^\circ$); reflex, sensory, or strength deficit in a pattern consistent with lumbar nerve root compression)

6.2.2 Enrollment, Baseline, and/or Randomization

6.2.2.1 Enrollment

This study uses a single informed consent document for both screening and treatment purposes. Thus the enrollment date is the date on which the consent document was signed and eligibility was confirmed. We anticipate that screening will be completed on the same day for the majority of participants because of the relatively simple and quick screening procedures required. At the latest screening will be completed within 7 days.

6.2.2.2 Baseline Assessments

Assessments involve collection of both mechanistic and self-report outcomes. Self-report

measures will be collected via REDCap (Research Electronic Data Capture), an NIH-supported, browser-based, software solution that allows researchers to create secure online forms for data capture, management and analysis. At each assessment participants will input data directly into REDCap. If a participant is unable to directly input data using a computer paper forms will be available with data uploaded at a later time.

The following assessments are collected at baseline:

- Demographic data will include age, sex, race/ethnicity, employment status and general medical and LBP history. Current medication use for LBP will be recorded. This information will be used for descriptive purposes and possible covariates in analyses.
- Physical examination will include spinal and hip range of motion and segmental mobility assessed with manually-applied posterior-anterior force.
- Oswestry Disability Index (OSW): a self-reported LBP-specific measure of function assessed on a 0-100 scale, with lower numbers indicating better function.
- Numeric Pain Rating Scale: a self-reported 0-10 rating of pain intensity ranging from '0' no pain, and '10' worst imaginable pain.
- Psychosocial Covariate Measures: will include Fear Avoidance Beliefs Questionnaire will be used to measure patients' beliefs about how physical activity and work may affect their LBP and perceived risk for re-injury. The Pain Catastrophizing and Pain Self-Efficacy short forms will be used to measure the extent to which people catastrophize in response to pain and their degree of confidence in the ability to function with pain respectively. These variables may serve as covariates in the analyses to control for psychosocial risk factors.
- Spinal Stiffness Measures: are obtained with a mechanically-assisted indentation device consisting of a motorized probe in an external frame. The probe contains a compressive-tension load cell. Displacement of the probe is measured by a linear variable differential transformer. Stiffness is assessed with the subject prone. The indentation probe is positioned over the L₃ spinous process. Indentation involves advancement of the probe from 5 N pre-load to 60 N final load maintained for 1 second. Three trials are performed with mean values used for analysis. Indentation data are used to calculate global stiffness (GS) (N) as the slope of the force displacement curve and terminal stiffness (TS) (N/mm) as the peak applied force and resultant displacement of underlying tissue.
- Lumbar Multifidus Activation Measures: are obtained with brightness-mode ultrasound images. The subject is prone with neck in neutral and arms overhead at about 120⁰ of shoulder abduction. Ultrasound transducer is placed just lateral to the spinal midline and angled medially until a parasagittal view of the multifidus at the L₄-L₅ and L₅-S₁ levels is obtained. Images are acquired at each level with the multifidus at rest and during submaximal contraction elicited by lifting the contralateral arm 2 inches while holding a weight proportional to body weight. Three images in each state are acquired and averaged. Muscle activation is calculated as change in thickness at rest and submaximal contraction.

6.2.2.3 Randomization

Following baseline assessment all participants will receive 2 SMT treatment sessions in the next week. Randomization to additional treatment will be done at the 1-week assessment. A randomization schedule will be developed prior to enrollment by co-investigator [name], Director of the Study Design and Biostatistics Center (SDBC) in the CCTS at the University of Utah. Blocked randomization with block sizes of 4 or 6 will be used. Randomization will be stratified based on site (Utah or Alberta) and responder status after 2 SMT sessions (based on re-assessment of the OSW) to balance these variables. At the 1-week assessment the study coordinator or research assistant will look up the participant in the study database and open the Responder & Randomization Status

form in REDCap. This form will display the Oswestry score from the baseline assessment and the calculation of score change. The percent change between baseline and 1-week scores determines responder status (>50% improvement = “responder”; <50% improvement= “non-responder”). Once the responder status is entered the study staff will select the randomize button on the screen to trigger study assignment based on the allocation table provided by the biostatistician, provided all of eligibility criteria are met and the participant has been assigned to one of the two study sites. If any of these criteria are not valid a warning message will be displayed indicating the criteria issue(s) and the randomization will not be completed.

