Individuals interested in participation will meet the site study coordinator to insure eligibility. Reasons for non-enrollment will be tracked. Eligible subjects choosing to participate will sign an informed consent document approved by the University of Utah or Alberta IRB, after which baseline examination procedures and completion of all eligibility assessments will be performed by a Research Assistant who will remain blinded to the subject's treatment group assignment throughout the study. Following baseline examination, all subjects will begin phase I treatment. All assessment and treatment sessions will be conducted at the Patient Wellness Center at the University of Utah and in the Rehabilitation Robotics Sandbox at the University of Alberta. Treatment will be provided by clinicians licensed to provide SMT (DC or PT) and trained in study-related procedures.

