6.2.3 Blinding

Participants cannot be blinded to study treatments. Randomization assignment will not be revealed until baseline examination, the first 2 SMT sessions, and the OSW assessment are complete to reduce potential bias by either the subject or research assistant. Follow-up assessments will be performed by a research assistant who will be blind to participants' treatment assignments. Participants will be reminded by the research assistant not to discuss aspects of their treatment during assessments. If a research assistant becomes unblinded during the course of a participant's study participation, he or she will not be allowed to conduct additional follow-up assessments for that participant. The research assistant may participate in assessments for other participants for whom blinding has not been compromised. Instances of unblinding during an assessment will be recorded as an unexpected event.

Clinicians providing treatment cannot be blinded. The use of standardized protocols for all treatments and clinician-compliance audits throughout the project will minimize potential bias related to differential treatment application.

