9.2.1 Treatment Assignment Procedures

A randomization schedule will be developed prior to enrollment by [name], Director of the Study Design and Biostatistics Center at the University of Utah. Blocked randomization with block sizes of 4 or 6 will be used. Randomization will be stratified based on site (Utah or Alberta) and responder status after 2 SMT sessions to balance these variables. Sequentially-numbered, sealed envelopes will be prepared containing treatment group assignments. The randomization envelope will be opened by the site Study Coordinator after completion of all baseline procedures and the 2 SMT sessions.

Subjects cannot be blinded to study treatments. Because our purpose is to optimize protocols, not to evaluate the SMT efficacy, we will not use placebos or attempt to balance clinician time. Randomization assignment will not be revealed until baseline examination, the first 2 SMT

sessions, and the OSW assessment are complete to reduce potential bias by either the subject or research assistant. Follow-up assessments will be performed by a Research Assistant who will be blind to subjects' treatment assignments. Clinicians providing treatment cannot be blinded. The use of standardized protocols for all treatments and clinician-compliance audits throughout the project will minimize potential bias related to differential treatment application. The PI at each site will be able to break the blinding if necessary for participant safety considerations.

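### Section 6.2.2.3 lets a research assistant trigger randomization, although research assistants must assess outcomes blind and section 9.2.1 gives allocation to the coordinator by sealed envelope

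*Combined protocol and SAP*

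**What the plan says.** Section 6.2.2.3 describes allocation through REDCap: "At the 1-week assessment the study coordinator or research assistant will look up the participant in the study database". That person opens the Responder & Randomization Status form, which shows the baseline Oswestry score and the change from it. Then: "Once the responder status is entered the study staff will select the randomize button on the screen to trigger study assignment". The allocation comes from a table supplied by the biostatistician.

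Section 9.2.1 describes allocation by sequentially numbered sealed envelopes and names one role: "The randomization envelope will be opened by the site Study Coordinator after completion of all baseline procedures and the 2 SMT sessions".

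On blinding, section 4.3 has the baseline examination done by a "Research Assistant who will remain blinded to the subject's treatment group assignment throughout the study". Section 6.2.3 says: "Follow-up assessments will be performed by a research assistant who will be blind to participants' treatment assignments". Section 10.1 again assigns the assessments to a blinded research assistant, with avoidance of bias as the reason. Section 6.2.3 adds that a research assistant who becomes unblinded does no further follow-up assessments of that participant but may go on assessing others. Unblinding during an assessment is recorded as an unexpected event.

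**The concern.** The role that section 6.2.2.3 allows to randomize is the role that three other sections require to be blind, and no sentence separates a randomizing assistant from an assessing one. Participants and treating clinicians know the assignment. Assessor blinding is therefore the main protection for whatever the assessor can influence, which includes parts of both co-primary outcomes of Primary Aim 1 (spinal stiffness and multifidus activation).

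The step falls at the 1-week visit, before the 4-week assessment that section 9.6 treats as primary and the 3-month assessment of persistence. An assistant unblinded at that step would be unblinded for both.

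**Working it through.** No plan figure bears on this point, so the check is a comparison of the text.

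1. **Who may allocate.** Section 6.2.2.3 names coordinator or research assistant for opening the form, then unspecified study staff for pressing the button. Section 9.2.1 names the coordinator only. The sections disagree on the role.

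2. **How allocation is done.** Section 6.2.2.3 uses a REDCap button drawing on an allocation table; section 9.2.1 uses sealed envelopes. Neither is described as a back-up for the other, so the sections also disagree on the method.

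3. **Who must be blind.** Sections 4.3, 6.2.3 and 10.1 all name the research assistant, and section 4.3 extends this over the whole study.

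4. **Whether randomizing reveals the assignment.** Not stated. The items that section 6.2.2.3 says the form displays are the Oswestry score, its change, and a warning if criteria fail. That the operator then sees the allocated group is a reasonable inference and is treated here as an assumption.

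5. **What follows if it does.** There are two branches. If the bar in section 6.2.3 is observed, another research assistant must do that participant's 4-week and 3-month assessments. The documents give no number of assistants per site and no handover. If the bar is not observed, those assessments are unblinded, against sections 4.3, 6.2.3 and 10.1.

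6. **Which outcomes are exposed.**
   - *Stiffness:* the examiner locates and marks L3 by hand and positions the probe (section 9.5.1). The indentation itself is motorized, from 5 N to 60 N, with three trials averaged.
   - *Multifidus activation:* the operator angles the transducer and acquires the images, but a blinded rater measures them offline (section 9.5.1).
   - *Physical examination:* repeated at 1 week, 4 weeks and 3 months (section 6.1).
   - *Oswestry and pain rating:* entered by the participant, who is not blinded (sections 6.2.2.2 and 6.2.3). Assessor blinding does little for these.

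7. **A second route to the assignment.** Under section 5.3 each participant's treatment-session forms in REDCap follow the randomized group. Under section 10.2 research assistants may enter data in REDCap. No access restriction is described, so an assistant who never presses the button might still see the group.

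**The case against.** The strongest reply is that the plan already contains the safeguard. Section 6.2.3 bars any research assistant who becomes unblinded from that participant's later assessments, in general terms and not only for accidents. Section 10.3.1 speaks of research assistants in the plural, so a blinded replacement is contemplated. If the rule is followed, the residue is a staffing matter and not bias. Section 9.2.1, read alone, keeps the assistant out of allocation altogether. Stiffness testing is largely mechanized, with a reported ICC of 0.98 to 0.99.

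Much of this stands. A reader might infer that the procedure unblinds the assessor for everyone, compromising up to 280 x 2 = 560 later assessments. The documents do not support that. The wording permits either role and requires neither; display of the assignment is not stated; the bar would remove an unblinded assistant; and section 9.2 itself assumes 92% retention at 4 weeks, or 0.92 x 280 = 257.6, about 258 participants. A reader might also set an assumed assessor shift against the detectable stiffness main effect of 0.37. No document supplies such a shift, and one common to all groups would cancel; only a shift that differs by treatment component biases a main effect.

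The safeguard still does not remove the conflict. An assistant who randomizes as written and sees the result is no longer blind, contrary to section 4.3. Observing the bar then means changing examiner between the 1-week measurement, which section 9.6 uses as the model baseline, and the primary 4-week measurement. The ICC quoted for stiffness is within and between days; section 9.5.1 gives no between-examiner figure. A change of examiner unrelated to group would add noise rather than bias, but the noise is avoidable.

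**Conclusion.** The point holds as an internal inconsistency. Section 6.2.2.3 permits a member of the assessing staff to trigger allocation, against the blinding statements in sections 4.3, 6.2.3 and 10.1 and against the role and method in section 9.2.1. Unblinding of an assessor is possible under the written procedure; it is neither required nor shown to occur.

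The conclusion about unblinding rests on one assumption, that the operator sees the assigned group. The disagreement between sections 6.2.2.3 and 9.2.1 on role and method needs no assumption. The exposure is confined mainly to L3 marking and probe positioning, image acquisition and the physical examination. Its effect on any estimate cannot be sized from the documents. It merits correction because it concerns part of the measurement of both mechanistic co-primary outcomes and the remedy is cheap.

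**What to change.** - In section 6.2.2.3, remove the research assistant as a permitted operator of the form, and replace the unspecified study staff with the site study coordinator or other staff who do no outcome assessments.
- Set REDCap user rights so that assessors cannot open the allocation field or the group-specific treatment-session forms.
- Reconcile sections 6.2.2.3 and 9.2.1 into one allocation method. If envelopes are only a back-up, say so and say when they are used.
- State that all 1-week measurements, including stiffness and multifidus activation, are complete before randomization. Section 9.6 implies this order, but the reveal condition in section 6.2.3 mentions only the Oswestry at that visit.
- If enrollment has begun, tabulate for each participant who triggered allocation and who did the 4-week and 3-month assessments, and report any overlap.

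The cost is a few sentences and a user-rights setting. Both sites have a coordinator, and that person already reviews the group-specific session forms at least monthly (section 5.3), so giving the step to the coordinator loses no blinding. The one practical drawback is that a coordinator, or another person who assesses no outcomes, must be available at each 1-week visit.

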6.2.3 Blinding

Participants cannot be blinded to study treatments. Randomization assignment will not be revealed until baseline examination, the first 2 SMT sessions, and the OSW assessment are complete to reduce potential bias by either the subject or research assistant. Follow-up assessments will be performed by a research assistant who will be blind to participants' treatment assignments. Participants will be reminded by the research assistant not to discuss aspects of their treatment during assessments. If a research assistant becomes unblinded during the course of a participant's study participation, he or she will not be allowed to conduct additional follow-up assessments for that participant. The research assistant may participate in assessments for other participants for whom blinding has not been compromised. Instances of unblinding during an assessment will be recorded as an unexpected event.

Clinicians providing treatment cannot be blinded. The use of standardized protocols for all treatments and clinician-compliance audits throughout the project will minimize potential bias related to differential treatment application.

6.2.4 Follow-up Visits

- Treatment Visits 1 and 2 (*completed within the 7 days following day 0*):
 - Spine stiffness and multifidus activation assessments pre- and post-SMT treatment
 - Treatment Session Form
- 1-Week Assessment (*completed from Day 7 – Day 12*):
 - Physical examination
 - Self-report questionnaires
 - Spine stiffness measures
 - Multifidus activation measures
 - Side effects questionnaire
- Treatment Visits 3 - 8 (*completed from Day 8 – Day 35, no more than 2 sessions/week*):
 - Treatment Session Form
- 4-Week Assessment (*completed from Day 29 – Day 42, 3 weeks after 1-Wk assessment*):
 - Physical examination
 - Self-report questionnaires
 - Spine stiffness measures
 - Multifidus activation measures
 - Side effects questionnaire

6.2.5 Completion/Final Evaluation

The final evaluation occurs 3 months after Baseline (*from Day 83 – Day 97*). The following assessments are performed at the final evaluation. If a participant wishes to terminate the study early, this is also the list of assessments we will attempt to complete at termination. Early termination will only be done at a participant's request or if a participant's risk-to-benefit ratio is substantially altered due to a change in status.

- Physical examination
- Self-report questionnaires
- Spine stiffness measures
- Multifidus activation measures

7. SAFETY ASSESSMENTS

Expected adverse events based on our prior experience and literature reports that may occur with the study interventions and assessments include the following:

- Increased back or spine pain intensity
- Muscle soreness
- Muscle spasms
- Psychological distress

7.1 Specification of Safety Parameters

Safety parameters intended to reduce risks for adverse events include having licensed clinicians specifically trained in the study procedures carry out all treatments. The spinal stiffness measurement procedure may be stopped at any time by the participant using a hand held switch. The potential risk of psychological distress from answering self-report questions about the impact of the individual's LBP on various aspects of his or her life will be minimized by telling participants that they are not required to answer any questions that are distressing.

7.2 Methods and Timing for Assessing, Recording and Analyzing Safety Parameters

The risk profile of the interventions in this study is minimal. Treatment procedures in the study are standard procedures used in everyday clinical practice and the measurement procedures have been applied by this research team in several preliminary studies.^{1,2} The use of manipulation for patients with acute LBP is supported by clinical practice guidelines in the United States³ and elsewhere, and is not associated with a high risk of serious side effects.⁴ Ultrasound measurement procedures are similar to those used during pregnancy, using low intensity ultrasound waves spread over a large area which causes very minimal heating that is mostly undetectable to the subject. The spinal stiffness measurement procedure uses a 60 N force to assess spinal stiffness. We have tested several hundred subjects with this procedure with no adverse events.²

